1. INTRODUCTION

Summary: BioKier, Inc. is developing colon-targeted, oral formulations of natural gut hormone secretagogues as non-prescription medical foods or supplements for nutritional use for improvement of insulin sensitivity in type 1 (T1D) and type 2 (T2D) diabetes. The natural compounds under investigation by BioKier are butyrate and L-glutamine. An earlier clinical study (CL-201), conducted at Pennington Biomedical Research Center, demonstrated that treatment for 4 weeks with the L-glutamine formulation (BKR-013) improved insulin sensitivity in a significant number of T2D subjects. BioKier now plans to investigate the effects of an oral butyrate tablet formulation (BKR-017) on insulin sensitivity and other metabolic parameters in diabetes patients; this study will be in T1D subjects. The long-term anti-diabetes effects of treatments that increase the presence of butyrate in the colon are well documented, which suggests that a colonic formulation of butyrate is a viable option for chronic use in both T1D and T2D. Along with L-glutamine, butyrate is one of the most active gut hormone secretagogues among natural compounds. Butyrate, a short-chain fatty acid, is the active ingredient of BKR-017 to be tested in the current clinical protocol (CL-301). The findings from the pilot study CL-201 with the L-glutamine capsule BKR-013 showed that insulin resistance is a relevant efficacy endpoint and therefore has been identified as the primary endpoint in this study.

Gut hormones, including glucagon-like peptide-1 (GLP-1), secreted by L-cells in the lower gut in response to nutrient stimulation, are important in the body's regulation of energy balance ¹. They signal the arrival of food in the gut to regulatory centers controlling glucose metabolism, appetite, and lipid metabolism. As well as regulating glucose homeostasis and satiety, an important effect of GLP-1 secreted from the gut is inhibition of fat absorption, which results in lower levels of free fatty acids and triglycerides in the circulation. Impaired secretion of gut hormones by L-cells in response to meals has been reported in obesity ^{2,3}, T2D ³, and T1D ⁴, although in these conditions the L-cells retain their ability to respond to secretagogues. Also, available evidence indicates that GLP-1 receptor agonists improve glycemic control when used in conjunction with insulin in patients with T1D ⁵, suggesting that augmented GLP-1 secretion can be beneficial in T1D. Butyrate is one of the most active natural L-cell agonists, as shown in *in vitro* ⁶⁻⁸ and has been shown to be an active secretagogue of GLP-1 in *in vivo* studies ⁸. There is a preponderance of human data demonstrating that the beneficial effect on diabetes of delivery of non-digestible carbohydrates to the colon are due to the actions of butyrate which is a product of fermentation of carbohydrates by colonic bacteria. Furthermore, the improvement in metabolic control after fermentation of ingested carbohydrates in the colon of rats ⁹ and humans ¹⁰ has been shown to be due to increased GLP-1 secretion. However, as effective as these approaches can be, they have not achieved wide therapeutic acceptance because the fermentation process causes serious GI side effects including diarrhea, bloating, and flatulence, which were not tolerated in clinical trials ¹¹. Alternate methods of delivering butyrate to the colon to achieve the same effects, but avoiding fermentation, were patented by BioKier.

In order to affect the metabolic conditions that result from impaired gut hormone secretion, BioKier has formulated the nutrient butyrate into a colon-targeted tablet formulation (BKR-017) intended to stimulate secretion of GLP-1 from L-cells in the lower gut. Butyrate delivered to the colon in tablet form will not cause the side-effects seen with formation of butyrate by fermentation.

It is well recognized in the scientific and medical community that stimulation of GLP-1 secretion by activation of L-cells in the lower gut is an area of expected dynamic development ¹²⁻¹⁴. BioKier is utilizing the GLP-1 secretagogue properties of butyrate to develop this safe, natural compound as a medical food. While a number of metabolic conditions result from GLP-1 dysregulation, BioKier is evaluating the effect of BKR-017 on insulin sensitivity in T1D patients. In this population, BKR-017 is not intended to treat T1D, and as such would not replace insulin therapy, but rather BKR-017 will provide a nutritional support to any currently prescribed T1D therapy, which may involve prescription medication, or diet and exercise, or both. Specifically, we expect that use of BKR-017 will afford better glucose control including reduced variability and reduced frequency of hypoglycemic episodes. This would be due to improved insulin sensitivity which is expected to lead to lower insulin use in those patients and would cause weight loss in patients with metabolic obesity. Another benefit of lowering insulin resistance would be to lower cardiovascular risk as there is plenty of evidence associating insulin resistance with increased CV risk ¹⁵. Elevated triglycerides are one of the validated risk factors for CV disease in both type 1 and type 2 diabetes patients ¹⁶, and one of the beneficial effects of metabolic surgery and colonic butyrate produced by fermentation is significant lowering of triglycerides and therefore reduction in CV risk ^{17;18}. Pertinently, GLP-1 receptor agonists ¹⁹ and DPP-4 inhibitors ²⁰ that elevate endogenous GLP-1 have been shown to decrease cardiovascular risk and inflammatory markers including triglycerides, free fatty acids, VLDL-C, apoB-48, and ApoB (reviewed in ²¹).

Butyrate, formulated as BKR-017 to target the colon, is being developed by BioKier as a medical food. Regulations require that medical foods be consumed or administered enterally under the supervision of a physician and that they are intended for the specific dietary management of a condition for which distinctive nutritional requirements, based on recognized scientific principles, are established by medical evaluation such as appropriate laboratory and clinical science. An Investigational New Drug (IND) application is not required to conduct clinical investigations of a medical food, and a New Drug Application is not required for marketing.

Previous studies conducted by BioKier, in which butyrate and L-glutamine was administered directly via infusion to the colon of T2D subjects, showed that single 1g doses of either butyrate or L-glutamine improved biomarker responses to an oral glucose challenge. Specifically, colonic administration of butyrate and L-glutamine both improved secretion of the glucoregulatory gut hormone GLP-1 and the subsequent insulin response. As follow-on to these effects observed on biomarkers, clinical outcome data is required to support marketing claims for BKR-017, the oral

formulation of butyrate, as a medical food, which would satisfy the FDA requirement of clinical data based on recognized scientific principles necessary for labeling a medical food. Note, in this study in T1D, it is not anticipated that improved GLP-1 secretion will necessarily increase insulin secretion but will improve insulin sensitivity, thus reducing insulin dose and glucose variability.

BioKier's Approach: While several nutrients have gut hormone secretagogue activity, BioKier has selected the nutrients butyrate and L-glutamine to formulate as candidates for medical foods to advance through clinical development. Although both have potent acute GLP-1-secretagogue activity, butyrate has well documented chronic effects on glucose regulation, including the reports of non-digestible carbohydrates improving metabolic control over the long term, discussed above. There is large body of scientific and clinical evidence supporting the role of butyrate in improving metabolic control in diabetes:

1. α -Glucosidase inhibitors, such as acarbose and miglitol, help control patients' glucose by shuttling saccharides to the colon where they are processed to butyrate and increase GLP-1 secretion ^{22,23}. That the increase in magnitude of improvement is in proportion to the increase in adverse gastrointestinal effects provides additional evidence that fermentation of saccharides to butyrate is the mechanism by which those drugs work and also why those drugs are not used, because of the adverse side-effects. An increase in colonic butyrate and augmented GLP-1 secretion were demonstrated in patients treated with those drugs.
2. Tagatose, which was in clinical trials ¹¹, produces butyrate in the colon by fermentation. Major outcomes after 1 year of tagatose dosing in this study were:
 - a. Mean HbA1c fell from 10.6% to 9.6%
 - b. Body weight declined from 108.4 to 103.3 kg
 - c. HDL cholesterol progressively rose from 30.5 to 41.7 mg/dL

However, Tagatose, which was in development as anti-diabetes drug by Spherix, was not commercialized due to side-effects of fermentation.

3. Oligofructose supplementation, which produces butyrate in the colon by fermentation, resulted in weight loss and better glucose control ²⁴. Also, insulin decreased in the oligofructose group and increased in the control group between initial and final tests ($P < 0.05$), indicating that insulin sensitivity improved with treatment.

BioKier has developed the colon-targeted tablet formulation, BKR-017, to deliver butyrate to the site of action in the colon. The dose of butyrate delivered is at least as large as the amounts of butyrate that are very effective for diabetes patients when produced from products that deliver saccharides to the colon. BKR-017 is designed to protect butyrate from digestion and absorption in the stomach and upper digestive system and deliver it to the colon where it can activate the secretion of gut hormones from L-cells. A safety advantage of targeting the luminal surface of the gut epithelium is that use of a compound such as butyrate, with local activity and very short systemic half-life, will result in negligible change to systemic levels and negligible off-target

effects. Accordingly, there should not be interference or interactions with other medications that are released in the small intestine or that circulate in plasma.

[REDACTED]

BioKier's Previous Studies - Pre-Clinical: BioKier has completed acute and chronic exploratory pre-clinical studies. The studies provided proof of the concept that butyrate was able to restore oral glucose-induced GLP-1 secretion when administered to the colon of diabetic rats and, when dosed chronically in an oral, colon-targeted, sustained-release formulation, prevented the development of diabetes in a rat diabetes model. Effects noted were a reduction in basal glucose levels and an improvement in insulin sensitivity ⁸.

BioKier's Previous Studies – Clinical: BioKier has conducted acute studies in T2D patients in which single doses of either butyrate or L-glutamine were administered to the colon of subjects in an enema solution. In diabetes drug-naïve patients, both butyrate and L-glutamine were effective in restoring oral glucose-induced secretion of GLP-1 and insulin to levels approaching those seen in non-diabetic controls ⁸.

BioKier has also conducted a 4-week clinical study (CL-201 at Pennington BioMedical Research Center) in T2D subjects to determine effect of an oral formulation of L-glutamine on glucose levels and insulin sensitivity. The exploratory clinical investigation employed a two-way crossover design, in which a BID dose of 1.5g L-glutamine in colon-targeted capsules (BRK-013), or placebo, were administered orally to T2D subjects. After 4 weeks of treatment with colon-targeted L-glutamine, which has the same mechanism of action as butyrate, there was an improvement in insulin sensitivity and lowering both fasting glucose and insulin in a significant number of patients. Significantly, in six of nine subjects there was a marked improvement in insulin sensitivity -- HOMA IR changed from 2.86 to 1.67 (n=6) in the responders, which compares favorably to 2.75 to 1.27 (n=10) reduction for bariatric surgery patients ²⁶. These data supported the concept that chronic delivery of a natural gut hormone secretagogue to the colon of diabetes patients has

potential as a therapeutic in T1D, as well as T2D, because metabolic surgery and colonic fermentation of carbohydrates is beneficial in both T1D and T2D.

Safety: Butyrate is a simple chemical entity, stable and readily available in United States Pharmacopeia (USP) grade and Active Pharmaceutical Ingredient grade (i.e., suitable for human use).

BioKier has conducted IRB-approved clinical studies of butyrate in T2D patients; notably, three single-dose infusion studies under Western IRB approval. Furthermore, a study done at the Mayo Clinic in 1993 investigated the effects of butyric acid and glutamine delivered directly to the colon of pouchitis patients by suppository²⁷. Butyric acid (4.4g bid and glutamine 1g bid) were given to patients for three weeks. The study reported positive effects on pouchitis but, significantly, found no safety issues of doses higher than those proposed by BioKier. In the combined clinical studies conducted by BioKier, there were 30 subjects exposed to 1g butyrate. Additionally, in a BioKier-sponsored study at the Mayo Clinic in which [name] was the Principal Investigator, 4 patients were treated with butyrate suppositories at 3g a day for 4 weeks with no adverse effects observed. Butyrate is also used as an enema in doses up to 8g for treatment of colon inflammatory conditions. Furthermore, the safety of butyrate supplementation of enteral or parenteral nutrition has been widely studied in chronic conditions (solid tumors) at doses of 14-28g/d. For Crohn's disease it was determined that 4 g/day butyrate as enteric-coated tablets for 8 weeks²⁸ was safe and well tolerated. Butyrate toxicity has been studied in humans and it was determined that dose-limiting toxicity was not identified²⁹. The escalation was halted at 200 mg/kg (of butyrin, a butyrate prodrug) three times daily (40 g per day) as further increases were felt to be not practical due to the large number of capsules which would need to be administered. In another study²⁷ butyric acid (4.4g BID) was given to patients for three weeks without any adverse effects. See Appendix 1 for human use summary.

A safety advantage of BKR-017 over administration of large oral or parental doses of butyrate is that it will lead to minimal systemic exposure to butyrate because it is released slowly, acts locally in the colon, and is metabolized quickly.

Rationale for the current study design: Butyrate was selected as a candidate compound based on clinical data from studies with non-digestible saccharides (tagatose, lactitol, and oligofructose), and α -glucosidase inhibitors; both approaches result in fermentation of saccharides by butyrogenic bacteria in the colon, producing butyrate and augmenting GLP-1 secretion. Long-term treatment with these products has been shown to be beneficial for diabetes patients, both T1D and T2D.

A BID dosing regimen was selected because the tablet core is designed to release butyrate in the ascending colon over a period of eight or more hours. This timing of the sustained-release profile suggests that BID dosing will be necessary to achieve optimal effects.

The 1.5g dose of BKR-017 was selected based on several factors including: safety data from BioKier studies and other relevant studies; practical considerations (three 500mg tablets was determined to be the highest number of tablets that could practicably be administered as a single dose); BioKier's efficacy data from single intracolonic dosing in which 1.0g was effective in increasing GLP-1, in diabetes drug-naïve patients; and on the relative activities of nutrients and gastrointestinal compounds reported in published studies. Considerations included:

1. Fiber producing ~1g of butyrate in the colon was effective in improving glucose regulation^{9,9} (BioKier anecdotal data).
2. Comparison of concentration of butyrate produced in the colon after use of maximal dose of acarbose and amount of butyrate release from BKR-017³⁰;
3. The amount of colon-infused bile acids effective in induction of GLP-1 secretion³¹; and
4. The amount of bile acids shuttled to the colon by Welchol³².

The proposed dose for this study has been increased from the 1.0-gram dose used in the single-dose studies to 1.5g to account for the lower concentrations of butyrate that will result from the sustained release profile of the BKR-017 tablets. Even at 1.5g BID (3.0g total daily dose), this dose is within the practical range for repeated dosing and well within dose and duration ranges safely administered in clinical studies and currently used in clinical practice (see Appendix 1: Previous human experience with butyrate [selected studies]).

Considering that BKR-017 will require chronic dosing to supplement a T2D patient's prescribed diabetes treatment in order to maintain adequate insulin sensitivity, longer-term safety should be taken into consideration. A seven -week duration of dosing was selected based on the safety data from reported clinical investigations (see Appendix 1) and this is within the duration of dosing of the butyrate in reported clinical trials. Furthermore, this duration of dosing was selected in order to cross reference the "placebo effect" observed in T2D patients. This placebo effect, which is known to affect daily glucose levels, has been shown to diminish by approximately 3 weeks³³. Therefore, in consideration of safety data and practical considerations a seven -week dosing regimen was selected.

2. STUDY PURPOSE AND OBJECTIVES

This study will test the hypothesis that delivery of the butyrate-containing BKR-017 tablet to the colon of T1D subjects will improve insulin sensitivity. Additionally, the effect of BKR-017 on triglycerides and glucose variability will be assessed. The safety and tolerability of repeat dosing (up to 48 days of administration) of BKR-017 will be determined. By exploration of the effects of BKR-017 on various metabolic biomarkers, the data generated from this study will be used to support continued evaluations of BKR-017 as non-prescription product for T1D patients requiring

nutritional support to improve cardiometabolic health. Furthermore, these data will support continued evaluation of BKR-017 for the regulation of weight and hypertriglyceridemia.

3. INVESTIGATIONAL PLAN SUMMARY

This study is an open-label study that will be conducted at Mayo Clinic. The total duration of subject involvement is approximately 11 weeks; 4-week Baseline Period which is followed by a 7-week Test Period. During the Test Period, subjects will self-administer three tablets of investigational product (BKR-017) two times daily: before breakfast and before bedtime.

4. STUDY POPULATION

4.1 Number of Subjects

Approximately 28 subjects with T1D will be screened to determine eligibility. Sixteen eligible subjects will be enrolled into the study with the expectation that 13 will successfully complete the study.

4.2 Method of Assigning Subject Numbers

All subjects who consent to participate in the study will be assigned a unique three-digit number (assigned sequentially, in chronological order beginning with number 301). The subject number will be assigned at Visit 1 (Day -28) and will identify the subject for the remainder of the study.

4.3 Inclusion/Exclusion Criteria

Inclusion Criteria:

1. Males and females between the ages of 20 and 80 years at the time of screening, inclusive
2. Diagnosed with T1D and under the care of a healthcare professional for its management
3. HbA1c 6.4-8.9%, inclusive
4. Has given written informed consent to participate in this study
5. Willing to complete 28-day baseline period and 48 -day test period
6. Willing to maintain current diet and exercise routine for the duration of the study
7. Current use of a Dexcom Continuous Glucose Monitor (CGM)

Exclusion Criteria:

1. History of bariatric or intestinal surgery
2. Active gastrointestinal disease including but not limited to irritable bowel syndrome, inflammatory bowel disease (e.g., Crohn's disease and ulcerative colitis), diverticulitis, gastroparesis, or chronic/frequent diarrhea or chronic/frequent constipation

3. Active and clinically significant hepatic, pancreatic disease, or renal disease as determined by the investigator
4. History of significant heart disease, including congestive heart failure, prior MI, chronic atrial or ventricular fibrillation, coronary artery disease, cerebral vascular disease, or other cardiovascular disease, that in the opinion of the investigator should exclude the subject from the study
5. Severely uncontrolled hypertension at screening defined as a systolic blood pressure > 180 mmHg or a diastolic blood pressure > 110 mmHg on the average of two seated measurements after being at rest for at least 5 minutes
6. Uncontrolled hyperthyroidism or hypothyroidism, or other significant thyroid disease
7. Active significant infection as determined by the investigator
8. Known allergy to butyrate or any of the components of the tablets
9. Participation in a clinical trial and/or treatment with an investigational drug during the 30 days before screening, or within 5 half-lives of receipt of an investigational drug or twice the duration of the biological effect of any investigational drug (whichever is longer)
10. Pregnant, nursing, or trying to become pregnant
11. Presence of pitting edema on physical exam
12. High fiber diet
13. In the investigator's judgment, the subject is not suitable for the study for any other reason or cannot commit to the requirements of the study.
14. Subject is taking one or more of the excluded therapies. See list of excluded therapies in section 4.4.

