Design: This study will test effect of BKR-017 (colon-targeted 500 mg butyrate tablets) as adjuvant therapy in type 1 diabetes (T1D) Subjects on metabolic control in this population. Insulin sensitivity, insulin usage, glucose control (variability), and triglycerides will be measured after 7 weeks of treatment and compared to Day -28.								
Number of Subjects: Assuming a 30% (approximate) early discontinuation rate, 16 Subjects will be consented and enrolled to ensure that 13 Subjects complete the 11-week study (4-week run in and 7 -week treatment period).								
Diagnosis and Main Criteria for Inclusion: Criteria for Subject recruitment will be: 20–80 years of age; type 1 diabetes with C-Peptide (CPR) less than 0.5 ng/mL; HbA1c level of 6.4–8.9%; at week -4. The study design will be a single-arm, open-label study. Subjects will be expected to use the Dexcom G6 Continuous Glucose Monitor (CGM) system and be willing to share their data via the CLARITY app with the study team.								
Duration of Subject Enrollment: Eleven (11) weeks; baseline period 28 days (4 weeks), treatment period: 48 days (7 weeks). Two visits will be required: one screen visit and one visit after 48 days of treatment.								
STUDY PERIOD (See Time and Events Schedule, Section 6)								
Baseline Period (Day -28):								
Visit 1 (Day -28): Following web- and phone-based pre-screening, subjects who remain eligible will be scheduled for a screening visit. Subjects will be asked to arrive for the screening visit (Visit 1) in a fasted state (10-hour fast). Subjects will be consented prior to obtaining any biological samples or performing any study procedures. Subject eligibility will be assessed, demographics, medical history, and concomitant medications will be obtained along with- height, weight, waist and hip circumference to calculate Hip-to-Waist Ratio (HWR), and an abbreviated physical exam will be performed (including signs for edema). Fasting samples will be obtained for glucose and triglycerides. Additional blood samples will be obtained for HbA1c, routine hematology, and routine chemistry assessments. Hypertension (HTN) will be determined from medical history and concomitant medications. Blood pressure will be measured and used, along with HbA1c, to calculate the eGDR (estimated Glucose Disposal Rate). A urine pregnancy test will be obtained for females of childbearing potential.								

CLINICAL PROTOCOL SYNOPSIS	Protocol No.:	CL-301

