
CLINICAL PROTOCOL SYNOPSIS		Protocol No.:	CL-301
Sponsor: Mayo Clinic		Investigator: [name]	
pregnancy test will be obtained for females of childbearing potential. The CGM sensor will be removed, and data downloaded.			
Subjects will be required to return the study CGM sensor, all unused test product in the original container along with any diary cards at this visit. The diary card and returned product will be reconciled by the study staff, and medication changes and adverse events recorded on the diary will be reviewed.			
Subjects with the following conditions will be excluded: History of bariatric or intestinal surgery, currently pregnant, nursing, or trying to become pregnant, type 2 diabetes, active gastrointestinal disease (e.g., irritable bowel syndrome, inflammatory bowel disease (e.g., ulcerative colitis, Crohn’s Disease, diverticulitis, gastroparesis, chronic/frequent diarrhea or chronic/frequent constipation), active and clinically significant hepatic, renal, or pancreatic disease, history of congestive heart failure, prior MI or significant cardiovascular disease, hepatic, renal, or pancreatic disease, history of congestive heart failure, prior MI or significant cardiovascular disease, uncontrolled hypertension uncontrolled hyper- or hypothyroid disease, active infection or history of trolled hypertension uncontrolled hyper- or hypothyroid disease, active infection or history of hepatic, renal, or pancreatic disease, history of congestive heart failure, prior MI or significant cardiovascular disease, uncontrolled hypertension uncontrolled hyper- or hypothyroid disease, active infection or history of chronic infection, subjects reporting an anticipated change in exercise or diet, subjects on a high fiber diet, subjects with pitting edema, and subjects who, in the investigator’s judgment, are not suitable for the study for any other reason, or subjects who cannot commit to the requirements of the study.			

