6. STUDY PROCEDURES

Table 1: Time & Events Schedule

	Pre-Screen	Baseline Period			Test Period				
		Visit 1							Visit 2
		D -28		D 0	D 18	D 28			D 48
Review of Eligibility & Study Requirements	X								
Written Informed Consent		X							
Review of Inclusion / Exclusion criteria		X							
Medical History & Demographics		X							
Blood Pressure (seated position at the start of visit)		X							X
Body Weight and Waist-to-Hip-Ratio		X							X
Hematology and Chemistry (including CPR)		X							X
Abbreviated Physical Exam		X							X
Urine Pregnancy Test (women of childbearing potential)		X							X
Dispense and/or Review Diaries for Compliance (Insulin and treatment)		X		X		X	X		X
Subject number assigned		X							
CGM sensors dispensed		X							
CGM sensor collected									X
Treatment Dispensed		X							
Fasting Glucose and Triglycerides		X							X
HbA1c		X							X
Exploratory Tests hs-CRP and 1,5AG		X							X
Concomitant Medication Review		X		X		X	X		X
Adverse Event Review				X		X	X		X

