6.2.1 Baseline Period (Day -28 to Day 0, Visit 1)

The screening visit will take place on Day -28 before midday at the Outpatient Clinic (OPC). The following will be performed:

1. Review of inclusion/exclusion criteria and eligibility
2. Subject consent will be obtained; documented with an Informed Consent Form (ICF) signed by subject. Written informed consent must be obtained before any study procedures are

performed and a record of the subject's consent (i.e., an original, signed and dated consent form) is to be maintained in the study files and a copy provided to the subject.

Subjects whose HbA1c is within the range of 6.4-8.9% and meet all other preliminary eligibility criteria will continue with all other screening procedures, as follows:

1. Urine pregnancy test for females of childbearing potential (exclude if positive and do not continue with other screening assessments).
2. Confirm that the subject is in a fasted state.
3. Obtain blood samples for routine hematology and chemistry tests, including CPR for safety evaluations, plus fasting glucose and triglycerides. See [Tables 3](#) and [4](#), [Appendix 2](#), for safety laboratory evaluations.
4. Demographics (date of birth, gender, race, and ethnicity).
5. Confirm medical history, including HTN determination, and including diabetes classification, onset/diagnosis date of diabetes, diabetes therapy(s), and therapy duration(s).
6. Obtain concomitant therapies (generic name, dose, route, frequency, date started, and reason for use).
7. Obtain vital signs (heart rate and blood pressure) in a seated position.
8. Obtain subject's height and weight
9. Obtain waist and hip circumference to calculate the WHR.
10. Perform standard physical exam including an exam to detect any signs of edema. Any amount of pitting edema will exclude a subject.
11. After signing consent and meeting all inclusion criteria, subjects will be instructed on, and supplied with a study provided Dexcom G6 sensors, to collect glucose data. Subjects will be instructed to keep their Dexcom CLARITY app active, so that glucose monitoring data can be accessed by the study team.

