7. SAFETY AND EFFICACY EVALUATIONS

7.1 Vital Sign Measurements

Single measurements of blood pressure and heart rate will be measured, with subjects in a seated position, at the start of every visit.

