7.3 Tests for Efficacy Assessments

7.3.1 Primary Efficacy Assessments

For the primary efficacy endpoint, HWR (Hip-to-Waist Ratio) and blood pressure will be measured at Day -28, Day 48 and used, along with HbA1c, to calculate the eGDR (estimated Glucose Disposal Rate) (WilliamsKV-ref 34).

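### The blood pressure exclusion is defined on the mean of two rested readings, but the measurement section prescribes one reading with no rest; the synopsis words the exclusion differently again

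*Combined protocol and SAP*

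**What the plan says.** Section 4.3, exclusion 5, reads "Severely uncontrolled hypertension at screening defined as a systolic blood pressure > 180 mmHg or a diastolic blood pressure > 110 mmHg", judged "on the average of two seated measurements after being at rest for at least 5 minutes". The criterion therefore fixes the limits, the position, the number of readings and the rest.

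The synopsis list of excluded conditions has only "uncontrolled hypertension uncontrolled hyper- or hypothyroid disease", with no severity, limit or method for the hypertension part.

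Section 7.1 sets the measurement procedure: "Single measurements of blood pressure and heart rate will be measured, with subjects in a seated position, at the start of every visit". It mentions no rest. The screening list in Section 6.2.1 asks staff to "Obtain vital signs (heart rate and blood pressure) in a seated position". The blood pressure row of Table 1 specifies a seated measurement at the start of the visit, on Day -28 and Day 48. Neither gives a number of readings or a rest period.

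Blood pressure also serves the primary endpoint. Section 7.3.1 says that it is "measured at Day -28, Day 48 and used, along with HbA1c, to calculate the eGDR", and the synopsis and Section 11.2 name it as an input too. Elsewhere, the synopsis takes hypertension from medical history and concomitant medications, Section 6.2.1 places its determination under medical history, and Section 12.4 lists it as a Y/N category. The eGDR equation is cited but not written out.

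**The concern.** An eligibility rule and the procedure that feeds it should describe the same measurement, and here they do not. A site that follows Section 7.1 to the letter has no value on which to document exclusion 5. A site that follows Section 4.3 departs from the letter of Section 7.1. Section 13.5 requires every deviation to be recorded and allows no waivers, so the choice should not be left to staff. The synopsis adds a second ambiguity, because uncontrolled and severely uncontrolled hypertension need not describe the same people.

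Two things are at stake. A safety exclusion may be decided on a different measurement from the one that defines it, and not the same way for every subject. In addition, if measured blood pressure enters eGDR, one reading per visit brings avoidable error into a paired comparison that expects 13 completers.

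**Working it through.** The plan states no figure on this point, so there is nothing to reproduce. The main check is a comparison of the sections.

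| Place | Definition of the exclusion | Readings | Rest |
|---|---|---|---|
| Synopsis | uncontrolled, undefined | not stated | not stated |
| Section 4.3 | severely uncontrolled, > 180 or > 110 mmHg | mean of 2 | at least 5 min |
| Section 6.2.1 | none | not stated | not stated |
| Table 1 | none | not stated | not stated |
| Section 7.1 | none | 1 | not stated |

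Only Section 4.3 mentions the second reading and the rest. The only procedural text that gives a number of readings gives one.

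**Eligibility (illustration).** The documents give no SD for a blood pressure reading. Assume a within-visit SD s of 4 to 10 mmHg, with normal and independent errors. For a true systolic pressure d mmHg below 180, the chance of a value above 180 is 1 − Φ(d/s) with one reading and 1 − Φ(d√2/s) with the mean of two.

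| d | s | One reading | Mean of two |
|---|---|---|---|
| 5 | 4 | 10.6% | 3.9% |
| 5 | 10 | 30.9% | 24.0% |
| 10 | 4 | 0.6% | 0.02% |
| 10 | 10 | 15.9% | 7.9% |
| 20 | 10 | 2.3% | 0.2% |
| 40 | 10 | about 0 | about 0 |

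By symmetry, the same figures give the chance that someone d mmHg above the limit is not excluded. The number of readings matters only near the limit. Section 4.1 expects about 28 people to be screened, and nothing in the documents suggests that many will be close to it.

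**eGDR input, if measured pressure is used.** Let b be the visit-to-visit SD, which averaging within a visit does not reduce. The error SD is √(b² + s²) for one reading and √(b² + s²/2) for the mean of two. A difference between two visits multiplies both by √2, so the relative reduction is the same for the change.

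| b | s | One reading | Mean of two | Reduction |
|---|---|---|---|---|
| 0 | 4 | 4.00 | 2.83 | 29% |
| 0 | 10 | 10.00 | 7.07 | 29% |
| 5 | 4 | √41 = 6.40 | √33 = 5.74 | 10% |
| 5 | 10 | √125 = 11.18 | √75 = 8.66 | 23% |
| 10 | 4 | √116 = 10.77 | √108 = 10.39 | 3.5% |
| 10 | 10 | √200 = 14.14 | √150 = 12.25 | 13% |

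These are reductions in the error of blood pressure, not of eGDR. The effect on eGDR cannot be computed without the equation. **If the Y/N status from history and medications is the input,** the number of readings has no effect on eGDR.

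**The case against.** The strongest reply is that exclusion 5 carries its own instructions. It names the occasion, position, number of readings, rest and limits. Section 6.2.1 does not cap the readings, and measuring at the start of a visit does not rule out a rest first. Staff checking eligibility at screening can simply follow Section 4.3. This stands against the inference, which a reader might draw, that the criterion cannot be applied. It does not remove the conflict with Section 7.1, which prescribes single measurements at every visit, screening included.

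Second, the two-reading rule governs eligibility at screening only. That is right: using it at Visit 2 is a recommendation for consistent measurement, not something Section 4.3 already requires.

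Third, a reader might infer that a chance reading near a category boundary could shift eGDR between visits. The documents do not support this. They give no equation and no boundary, and no section derives a hypertension category from the study reading. They describe either measured pressure or a status taken from history and medications.

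Fourth, it is tempting to say that averaging halves the error variance. That holds only for the within-visit part; visit-to-visit variation also enters a comparison of visits about 11 weeks apart.

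Finally, the synopsis is a condensed list with an older version date than the protocol, and its text is partly garbled, perhaps from extraction. This makes the synopsis mismatch largely editorial. The difference between undefined uncontrolled hypertension and a defined severe form still needs reconciling.

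**Conclusion.** The inconsistency is real and lies in operative text: the measurement procedure as written does not produce the value that exclusion 5 requires, and the synopsis states the exclusion differently. Severity is minor. The effect on eligibility is limited to subjects near the limits, likely few of about 28.

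The effect on the primary endpoint is conditional. If measured pressure enters eGDR, as Sections 7.3.1 and 11.2 and the synopsis indicate, two readings lower the error SD of that input by 29% with no visit-to-visit variation, and by about 3.5% to 23% with the assumed SDs of 4 to 10 mmHg within visits and 5 to 10 mmHg between them. If the Y/N status enters, the effect on eGDR is nil. All these SDs are assumptions, and any benefit of the rest period itself is not quantified.

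**What to change.** - Reconcile the synopsis, Sections 4.3, 6.2.1 and 7.1, and Table 1 on the definition of the hypertension exclusion, the number of readings and the rest. Which definition or limit is right is for the sponsor and investigator; this review takes no position on it.
- Align Section 7.1 with the two rested seated readings that Section 4.3 already requires at screening. Use the same method at Visit 2, so that blood pressure is measured identically at both eGDR time points. Record both readings.
- State whether measured blood pressure or Y/N hypertension status enters eGDR.

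The cost is a few minutes per visit with existing staff and equipment, one extra eCRF field, and the text changes in an amendment.
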